## **5.0 Treatment of participants**

Participants will receive eight week of open-label glecaprevir (300mg)/pibrentasvir (120mg) in an oral once-daily fixed dose. Dose modifications are prohibited.

### **5.1 Method of Assigning Participants to Treatment Groups (Randomisation)**

At the Screening Visit, all participants will be assigned a screening ID.

For participants who meet the study selection criteria and are enrolled in the study, the site personnel will assign a Participant ID number which will then be retained by the participant for the duration of the study. The site personnel will randomise the participant to one of the two treatment groups at baseline via the study randomisation system.

Randomisation will be 1:2 (standard:simplified). Randomisation will be using blocks and will be stratified by country and genotype (1 vs non-1).

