## 1.0 Background and rationale

Chronic hepatitis C virus (HCV) treatment was interferon-based for two decades, with the addition of ribavirin (RBV), Pegylated interferon (PEG-IFN), and initial protease inhibitor direct acting antiviral (DAA) therapies (telaprevir, boceprevir) providing stepwise improvements in the rate of sustained virological response (SVR). Despite these improvements in interferon-containing regimens, treatment uptake remained low in most countries, ranging from <1% to a maximum of 5% of people with chronic HCV initiating therapy each year.

Fortunately, recent years have seen a revolution in HCV therapeutic development, in particular the interferon-free direct acting antiviral (DAA) regimens. Short, simple (once daily dosing oral regimens), highly tolerable, short-duration (8-12 weeks) therapy with pangenotypic potency and extremely high efficacy (cure rates above 95%) will soon be the norm. The broad implementation of such therapeutic regimens has the potential to produce one of the major turnarounds in disease burden seen in public health and clinical medicine.

The capacity to scale-up interferon-free DAA therapy would be enhanced by simplified treatment monitoring strategies. The “next generation” DAA regimen of glecaprevir (300mg)/pibrentasvir (120mg), a protease inhibitor and NS5A inhibitor, provides key features for HCV treatment simplification, including on-treatment monitoring: 1) pangenotypic activity with extremely high efficacy (SVR>95%); 2) no relationship between time to undetectable HCV RNA and SVR; 3) minimal drug-related toxicity; 4) ease of dosing (three pills once daily); and short duration (8 weeks in non-cirrhosis and 12 weeks in cirrhosis for treatment naïve patients). In phase II and III clinical trials in patients without cirrhosis, 8 weeks of glecaprevir (300mg)/pibrentasvir (120mg) has provided intention-to treat SVR rates of 99.1%, 98%, 97%, and 93.1% in genotype 1, 2, 3, and 4-6 populations, respectively with extremely low rates of drug-related toxicity.

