### **10.3 Efficacy analysis**

The primary analysis will compare the randomised treatment arms on an ITT basis (see section 10.4). The primary efficacy endpoint is the proportion of patients with undetectable HCV RNA at 12 weeks post end of treatment. The treatment arms will be considered non-inferior if the lower limit 95% CI of the difference between the two arms does not exceed -6%. There will be no extrapolation of data for the primary endpoint. Patients with missing data will be analysed as missing equals failure. Secondary analyses will compare randomised treatment groups based on available data (mITT Population).

For all secondary endpoints simple pairwise comparisons of the randomised treatment arms will be undertaken for both the ITT and mITT populations.

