### **10.5 Definition of Intent-to-treat Population**

Intent-to-treat (ITT) and modified intent-to-treat (mITT) populations will be used for efficacy analyses. All patients who receive at least one dose of study drug will be included in the ITT population (and safety population). The mITT population will exclude patients who have completed treatment (>95% adherence) (according to phone contact at week 8), but have not returned for their SVR12 assessment. The data from the ITT and mITT will be presented by the treatment arm assigned at the time of randomisation. For the primary analyses of non-inferiority tests, the percentage of patients achieving SVR12 in each arm will be calculated with confidence intervals (CI) using the normal approximation to the binomial distribution.

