## **GENERAL CONSIDERATIONS FOR DATA ANALYSES**

### **Statistical Methods**

Analysis results will be presented using descriptive statistics. For categorical variables, the number (n) and percentage of participants in each category will be presented. For continuous variables, the number of participants (n), mean and standard deviation (SD), median, interquartile range (IQR, Q1-Q3), range (minimum, maximum) will be reported; for inclusion in the manuscript, an appropriate determination will be made depending on the variable, size and distribution of the population studied. Statistical tests will be 2-sided and performed at the 5% significance level, unless specified. For the analysis of categorical outcomes, Chi-squared tests or exact equivalents (for small numbers) will be used. For comparison of continuous measures, t tests or non-parametric equivalents will be used as appropriate for the observed data distribution.

For the primary analysis of non-inferiority, the percentage of participants achieving SVR12 in each arm and the difference in percentages of participants achieving SVR12 between study arms will be calculated with confidence intervals using the normal approximation to the binomial distribution.

Non-inferiority of the 8-week regimen of glecaprevir/pibrentasvir with a simplified monitoring strategy to the 8-week regimen of glecaprevir/pibrentasvir with a standard monitoring strategy with regard to the proportion achieving SVR12 will be shown if the lower bound of the confidence interval for the differences is above the non-inferiority margin of -6 percentage points.

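### Randomisation is stratified by country and genotype, but the primary SVR12 difference and its confidence interval ignore the strata, so the interval is very slightly wider than it need be

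*Protocol*

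**What the plan says.** Protocol 5.1 states that randomisation is in blocks and "will be stratified by country and genotype (1 vs non-1". Allocation is 1:2, standard to simplified.

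The primary comparison names no strata, weights or covariates:

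- Protocol 10.3: "The primary analysis will compare the randomised treatment arms on an ITT basis". Non-inferiority is judged by whether the "lower limit 95% CI of the difference between the two arms does not exceed -6" percentage points.
- Protocol 10.5 describes the SVR12 percentages by arm, which "will be calculated with confidence intervals (CI) using the normal approximation to the binomial distribution".
- SAP, Statistical Methods, adds that "the difference in percentages of participants achieving SVR12 between study arms will be calculated with confidence intervals", by the same normal approximation.

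Genotype returns in the SAP only as by-arm reporting with exact intervals (Secondary efficacy endpoints) and as rows of the subgroup table (Table 12). Country enters no analysis. The SAP's Baseline Data section plans a sensitivity analysis if a large baseline difference is seen, but it does not tie this to the stratification factors. Neither document gives a reason for leaving the strata out of the primary comparison.

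**The concern.** Blocked allocation within strata balances the arms on the stratifying factors, so differences between strata largely drop out of the arm comparison. A pooled binomial variance still counts those differences as noise. If the strata predict outcome, the reported interval is then a little wider than the design warrants.

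The protocol's background suggests that genotype does predict outcome, citing "SVR rates of 99.1%, 98%, 97%, and 93.1% in genotype 1, 2, 3, and 4-6 populations". The primary conclusion depends on one confidence limit set against -6 points, in a trial planned at about 80% power, so even a small avoidable widening deserves a look. There is also a pre-specification issue: with the SAP silent, a stratified result could be produced later, and it might fall on the other side of the margin from the crude one.

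**Working it through.** **Inputs from the documents.** 125 standard and 250 simplified; SVR12 96% in both arms; margin 6 points; two-sided 95% interval (Protocol 10.1 and 10.3; SAP, Sample size and power). Prior SVR by genotype: 99.1% (1), 98% (2), 97% (3), 93.1% (4-6) (Protocol 1.0).

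**Assumed, not in the documents.** Genotype 1 share w of 30-70%; the genotype mix within non-1; number of countries and their SVR12 rates.

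**Step 1: reproduce the stated power, unstratified.** Let k = 1/125 + 1/250 = 0.012.

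- SE = sqrt(0.96 × 0.04 × 0.012) = 0.02147; half-width 1.96 × SE = 4.21 points.
- Power = Φ(0.06/0.02147 − 1.96) = 79.8%.

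This agrees with the stated figure of about 80%, so the sample size took no credit for stratification.

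**Step 2: remove the between-genotype variance.** With genotype 1 rate p1, non-1 rate p2 and p̄ = w·p1 + (1−w)·p2:

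- crude variance = p̄(1−p̄)·k
- stratified variance = [w·p1(1−p1) + (1−w)·p2(1−p2)]·k

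Worked case, w = 0.5, 99.1% v 93.1%: p̄ = 0.961. The crude term is 0.961 × 0.039 = 0.03748. The within-stratum term is 0.5 × 0.991 × 0.009 + 0.5 × 0.931 × 0.069 = 0.03658. The reduction is 2.4%.

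| w | p1 v p2 | Variance reduction | Half-width (points) | Power |
|---|---|---|---|---|
| 0.3 | 99.1% v 97% | 0.4% | 3.27 → 3.26 | 95.0% → 95.0% |
| 0.5 | 99.1% v 97% | 0.6% | 2.97 → 2.96 | 97.7% → 97.8% |
| 0.5 | 97.5% v 94.5% (assumed; mean 96%) | 0.6% | 4.21 → 4.20 | 79.8% → 80.0% |
| 0.3 | 99.1% v 93.1% | 1.6% | 4.72 → 4.69 | 70.2% → 70.9% |
| 0.5 | 99.1% v 93.1% | 2.4% | 4.16 → 4.11 | 80.8% → 81.7% |
| 0.7 | 99.1% v 93.1% | 2.9% | 3.48 → 3.43 | 92.2% → 92.9% |

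Baseline power varies between rows because p̄ does; only the change within a row matters. A variance reduction of 0.4-2.9% is worth about 2 to 11 of 375 participants (0.004 × 375 = 1.5; 0.029 × 375 = 10.9).

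**Step 3: country, on assumed rates only.** Eight equal strata averaging 96%: rates from 89% to 100% give 4.21 → 4.13 points and 79.8% → 81.3% power; rates from 86% to 100% give 4.21 → 4.08 points and 79.8% → 82.2%.

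**Step 4: simulation of the decision rule** (100,000 trials per scenario, half genotype 1 assumed).

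- The crude and stratum-weighted estimates had the same empirical SD. Only the variance formula differs.
- Mantel-Haenszel with Sato variance, genotype only at 99.1% v 93.1%: mean full width 8.17 → 8.07 points, power 84.7% → 85.1%, one-sided error 1.9% → 2.1%.
- The same with eight assumed countries (16 cells): mean full width 8.63 → 8.49 points, power unchanged, error 2.0% → 2.2%.
- A plug-in stratified Wald interval over 16 sparse cells: error about 2.7%, coverage 93.6-93.7% at a true difference of -6 points.
- The crude rule with no stratum effect at all (96% v 90%): one-sided error already about 2.0-2.1%.

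**The case against.** The strongest reply is that an unadjusted risk difference is valid after stratified randomisation, errs on the safe side here, and matches the way the trial was sized. All of that stands.

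It is also fair to say that the upper end of the gain uses an unlikely contrast. The stratum is non-1 as a whole, and a rate of 93.1% there would require every non-1 participant to be genotype 4-6. Genotypes 2 and 3, at 98% and 97%, sit in the same stratum. At a non-1 rate of 97-98% the variance share is only about 0.15-0.6%. In some simulated scenarios power did not rise at all.

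The fix is not wholly free either. With about 15 failures expected (0.04 × 375), country-by-genotype cells will be sparse, and a poorly chosen stratified interval would do worse than the present rule. This limits which interval to use, but it does not remove the case for stratifying: the Sato interval kept its error below 2.5% with 16 cells.

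The planned by-genotype tables and the imbalance-triggered sensitivity analysis do not answer the point. The tables contain no stratified comparison between arms. The sensitivity analysis depends on a large observed imbalance, which stratification makes unlikely for genotype, and it leaves the primary estimator as it is.

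**Conclusion.** The mismatch between design and analysis is real, and both documents are silent on it. Its effect is minor. Genotype accounts for about 0.01-0.05 points of half-width and 0 to about 1 point of power, on the protocol's genotype rates, a non-1 rate between 93.1% and 97%, and an assumed genotype 1 share of 30-70%. Any country contribution is conjecture until rates are known.

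A reader might infer more, and the documents do not support it:

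- *That ignoring the strata is why the test runs below 2.5%.* Most of the shortfall is present with no stratum effect and comes from the Wald interval with few events.
- *That the interval is too wide overall.* At 96% in both arms the crude interval covers about 94%. The excess width concerns this one variance component.
- *That the point estimate loses precision.* It does not. Stratified allocation already benefits the estimate, and only its stated variance misses the credit.
- *That the sample size or power statement is wrong.* It reproduces at 79.8% without stratification.

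This is a worthwhile refinement, not a threat to the trial's conclusion.

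**What to change.** In SAP Statistical Methods, define the primary SVR12 difference (simplified minus standard) as a Mantel-Haenszel stratum-weighted risk difference with a Sato or stratified Miettinen-Nurminen 95% interval. Rule out a plug-in stratified Wald interval. Stratify by genotype (1 v non-1) and by country, pooling small countries by a rule fixed before database lock. Apply the -6 point criterion to that interval in the ITT population and in the mITT and per-protocol repeats, and report the crude difference as supportive.

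If the sponsor prefers to keep the crude difference as primary, the SAP should say so, give the reason, and pre-specify the stratified analysis as a sensitivity analysis.

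The cost is a paragraph of SAP text and a few lines of code. Both factors are already recorded at randomisation, and the margin, sample size and conduct do not change. The one real burden is the pooling rule, which must be settled without reference to outcomes because so few failures are expected.

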## **5.2 Study Drug and Study Visit Adherence**

Treatment will be administered in four-weekly supply for standard arm participants and eight-weekly supply for simplified arm participants.

All participants will be required to return the study drug to the site at the SVR12 visit. Participants in the standard arm will be instructed to only return all study medication at SVR12 to provide standardised drug accountability assessments across the two arms.

Treatment adherence will be also recorded through an adherence questionnaire completed at Week 4 and EoT via the phone-contact visits as described in section 6.2. Study visit adherence will be recorded in the eCRF.

## **5.3 Prior and Concomitant Medications**

Concomitant medication must be recorded in the source documents and eCRF from screening until the SVR12 visit.

Subjects must be able to safely discontinue any prohibited medications or supplements listed in 1 at least 14 days or 10 half-lives (whichever is longer) prior to the first dose of glecaprevir/pibrentasvir and not use these during the entire Treatment Period and for 14 days following discontinuation of study drugs.

**Table 1. Contraindicated and non-recommended concomitant medications with glecaprevir/pibrentasvir**

Drug Class	Drug(s) within Class that are contraindicated/not recommended	Clinical Comments
Antiarrhythmics	Digoxin	Digoxin dose should be reduced by 50% when coadministered with glecaprevir/pibrentasvir.
Anticoagulants	Dabigatran etexilate	Use of glecaprevir/pibrentasvir may increase dabigatran exposure, therefore concomitant use is not recommended.
Anticonvulsants	Carbamazepine, phenytoin, phenobarbital	May decrease DAA exposure leading to a potential loss of therapeutic activity, therefore not recommended.
Antihistamine	Astemizole Terfenadine	Exposures to Astemizole and Terfenadine may be increased, therefore not recommended.
Antimycobacterial	Rifampin Rifabutin	May decrease DAA exposure leading to a potential loss of therapeutic activity, therefore not recommended.
Ethinyl estradiol-containing products	Ethinyl estradiol-containing medications (such as combined oral contraceptives and hormone replacement therapy)	Potential for ALT elevations, therefore not recommended.
Gastrointestinal pro-kinetic agent	Cisapride	It is a CYP3A4 substrate. Concomitant use is not recommended.
Herbal Product	All herbal supplements (including milk thistle) St. John's Wort ( Hypericum perforatum ) Red yeast rice (monacolin K)	May decrease DAA exposure leading to a potential loss of therapeutic activity, therefore not recommended.
HIV non-nucleoside reverse transcriptase inhibitor	Efavirenz Etravirine Nevirapine	May decrease DAA exposure leading to a potential loss of therapeutic activity, therefore not recommended.
HIV protease inhibitor	Tipranavir/ritonavir Atazanavir Colbicistat Boosted PIs Darunavir Fosamprenavir Indinavir Lopinavir Ritonavir Saquinavir	May increase DAA exposure, therefore not recommended.
HMG-CoA Reductase Inhibitors *	Atorvastatin Lovastatin Simvastatin Pivastatin	Potential for myopathy including rhabdomyolysis., therefore not recommended.
Chronic systemic immunosuppressants	Corticosteroids (prednisolone equivalent of >10mg/day for >2 weeks) Azathioprine Monoclonal antibodies	
Strong CYP3A inducers	Carbamazepine	

\* Some HMG-CoA reductase inhibitors (including atorvastatin, lovastatin, or simvastatin) should not be taken with glecaprevir/pibrentasvir. Participants receiving these statins should either switch to pravastatin or rosuvastatin prior to the first

dose of study drug or interrupt statin therapy throughout the treatment period and until 30 days after the last dose. If switching to or continuing pravastatin or rosuvastatin, it is recommended to reduce the pravastatin dose by 50% or limit the rosuvastatin dose to 10 mg daily while on treatment.

Post-menopausal hormone replacement therapy i.e., estradiol, esterified or conjugated estrogens, as long as they do not contain ethinyl estradiol, may be used with glecaprevir /pibrentasvir at the discretion of the Investigator.

Glecaprevir /pibrentasvir is not recommended for use in patients requiring stable cyclosporine doses > 100 mg per day.

Use of investigational agents or devices for any indication within 2 weeks or 10 half-lives, whichever is longer, prior to study drug administration is contra-indicated.

Should any participant need to initiate treatment with any contra-indicated medication during the study, the Medical Monitor must be consulted prior to the initiation of any contra-indicated medication. In the event that a contra-indicated medication is initiated prior to discussion, the Medical Monitor must be made aware of the use of the contra-indicated medication as soon as possible. Medical Monitor's contact details are listed on the cover of this protocol.

#### **5.4 Methods of contraception:**

Women of Childbearing Potential must practice at least one of the following methods of birth control from baseline (or earlier) through at least 30 days after the last dose of study drug (postmenopausal or permanently surgically sterile women are excluded).

- Progestogen-only hormonal contraception (oral, injectable, implantable), initiated at least 1 month prior to Study Day 1.
- Bilateral tubal occlusion/ligation (if via hysteroscopy [i.e., Essure], provided that a hysterosalpingogram confirms success of the procedure)
- Vasectomized partner(s), provided the vasectomized partner verbally confirms receipt of medical assessment of the surgical success, and is the sole sexual partner of the WOCBP trial participant.
- Intrauterine device (IUD).
- Intrauterine hormone-releasing system (IUS).
- Male or female condom with or without spermicide.
- Cap, diaphragm or sponge with spermicide.

- A combination of male condom with either cap, diaphragm or sponge with spermicide (double barrier method).
- True abstinence: Refraining from heterosexual intercourse when this is in line with the preferred and usual lifestyle of the subject [periodic abstinence (e.g., calendar, ovulation, symptothermal, post-ovulation methods) and withdrawal are not acceptable].

There are no specific contraception requirements for male participants.

## 6.0 Study procedures

### 6.1 Visits and Procedures

The following assessments must be conducted at study visits as per the schedule of assessments:

Vital signs & physical measurements	Sitting systolic and diastolic blood pressure, heart rate, body weight a , height a
FibroScan ®	Transient elastography; within 6 months prior to screening. Use APRI in the absence of FibroScan ®
Biochemistry	Creatinine, sodium, chloride, potassium and BUN
Liver Function Tests	ALT, AST, GGT, total bilirubin, albumin, alkaline phosphatase, total protein
Full Blood Count	Haemoglobin, haematocrit, White Blood Cells, platelets, neutrophils
Clotting	INR
Urinary Drug Screen	Screen for Opiates (other than methadone and buprenorphine), Amphetamines and Cocaine
HCV RNA	Must be quantitative at Screening
HCV Genotype	Within 5 years prior to screening
HIV Serology	Anti-HIV Ab
HBV Serology	HBsAg
HCG Pregnancy Test	For women of childbearing potential, a negative urine (or serum) HCG test at screening and baseline
Questionnaires	Adherence survey, EQ-5D-3L, Practitioner Acceptability Questionnaire, Participant Satisfaction Survey

a at screening only

The following assessments and procedures must be performed at each visit as specified below:

#### Screening visit (Week -6 to Week 0) - All participants

- Informed consent
- Medical history and patient demographics
- Concomitant medication

- Vital signs and physical measurements
- Health outcome survey (EQ-5D-3L)
- Participant Satisfaction survey
- Fibroscan®
- HCV RNA and genotype (Local Lab.)
- LFTs, FBC and biochemistry (Local Lab.)
- HIV antibody & HBV serology (Local Lab.)
- Clotting (INR)
- UDS
- Pregnancy test (females of child bearing potential only)
- Research specimen collection (Central Lab.):
  - EDTA plasma & whole blood (at all sites)
  - PBMCs (at selected sub-study sites only)

#### **Baseline visit (Week 0) - All participants**

- Vital signs and physical measurements
- LFTs, FBC and biochemistry (Local Lab.)
- Pregnancy test (females of child bearing potential only)
- Adverse Events
- Concomitant medication
- Research specimen collection (Central Lab.): EDTA plasma
- Randomisation
- Study drug dispensed (4-weekly supply for standard arm participants and 8-weekly supply for simplified arm participants)

#### **Week 4 – All participants**

Via phone contact 1-2 days prior to week 4. A maximum of three attempts should be made by the site personnel to contact the participant over the phone. Phone contact attempts must be within the visit window allowed per protocol. All attempts must be recorded in the source documents.

- Adverse Events
- Concomitant medication
- Adherence survey

In addition to the above the following assessments will be completed at week 4:

	Standard treatment monitoring group	Simplified treatment monitoring group
HOME	Completed at HOME by the participant: NIL	Completed at HOME by the participant: 
 
• Pregnancy test (females of child bearing potential only)
 

CLINIC	Completed at the CLINIC : 
 
• Vital signs and physical measurements
 
• LFTs, FBC and biochemistry (Local Lab.)
 
• Pregnancy test (females of child bearing potential only)
 
• Research specimen collection (Central Lab.): 
 
• EDTA plasma (at all sites)
 
• PBMCs (at sub-study sites only)
 
 
 
• Study drug dispensed (4-weekly supply)
 
	Completed at the CLINIC : NIL – participant is not required to attend the clinic

